8.2.2.2 Vineland Adaptive Behavior Scale

The Vineland Adaptive Behavior Scale, 3rd Edition (VABS-3) caregiver interview form will be used to evaluate communication, socialization, and daily living skills of subjects to assess their overall adaptive functioning. This assessment is an interview of the caregiver by a trained qualified rater.

Change from baseline in standard VABS domain scores (consisting of adaptive behavior composite, communication domain, daily living skills domain and socialization domain) and raw scores and v-scores for subdomains (Receptive, Expressive, Written, Personal Care, Domestic, Community, Interpersonal Relationships, Play and Leisure Skills, and Coping Skills) collected in the eCRF will be summarized and analyzed for Week 6 and Week 12, as described in [Section 8.1](#).

Missing data convention from the provider will be used for missing assessments and scores. Otherwise, missing data from the assessment will be kept as missing.

Missing data convention from the provider will be used for missing assessments and scores. Otherwise, missing data from the assessment will be kept as missing.

8.2.2.3 Pediatric Sleep Clinical Global Impressions Scales

The Pediatric Sleep CGI scales were recently developed to measure pediatric insomnia in autism spectrum disorder and have been validated against the CSHQ and actigraphy ([Malow et al 2016](#)). Questions include the subject's ability to fall asleep and remain sleeping independently (i.e., apart from LAR/caregivers); bedtime resistance; sleep onset delay; night awakening; LAR/caregiver satisfaction with their child's current sleep patterns; family functioning, as affected by their child's current sleep patterns; and clinician's overall concern with the child's sleep.

Pediatric Sleep CGI severity questions will be analyzed for Week 2, Week 6, and Week 12, as described in [Section 8.1](#).

Missing data convention from the provider will be used for missing assessments and scores. Otherwise, missing data from the assessment will be kept as missing.

8.2.3 Direct Subject Assessment Endpoints

8.2.3.1 Actigraphy

Actigraphy is a noninvasive method of monitoring human rest/activity cycles. A small actigraph unit is worn to measure daytime and sleep activity. The actigraph unit stores motion data by clock time, and the data must be uploaded to an actigraphy database for analysis. The actigraphy data (including parameters such as: SOL, WASO, TST, NA, sleep efficiency, daily activity level, and sleep fragmentation) will be compared to the sleep diary data. The derivation of these parameters will be as follows:

Sleep Parameters	Derivation
Sleep Onset Latency (SOL)	Mean of Onset Latency (minutes), duration from the beginning of the rest period to the start of sleep onset, reported when interval type = sleep
Total Sleep Time (TST) during night	Take Sum of sleep time (minutes) where interval type = 'sleep' within each day then the Mean of this sum for an average score per day. Convert its unit to hours in analysis.
Total Sleep Time (TST) during day	Take Sum of sleep time (minutes) where interval type = 'Active' within each day then the Mean of this sum for an average score per day. Convert its unit to hours in analysis.

Wake After Sleep Onset (WASO)	Mean of WASO when interval type = sleep
Nocturnal Awakenings (NA)	Mean of # Wake bouts when interval type = sleep
Sleep Efficiency	Mean of Efficiency (%) when interval type = sleep. Efficiency is defined as total sleep time as a fraction of the rest period (total time in bed).
Daily Activity Level	Take Sum of Total AC (counts) within each day then the Mean of this sum for an average score per day
Sleep Fragmentation	Sum of Fragmentation (%+%) when interval type = sleep

The baseline values of actigraphy parameters will be obtained from data collected within 7 days immediately preceding Day 1.

The change from baseline in the subject actigraphy parameters will be analyzed for Week 2, Week 6, and Week 12, as described in [Section 8.1](#).

Missing data convention from the provider will be used for missing assessments and scores. Otherwise, missing data from the assessment will be kept as missing.

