1.4 Clinical Experience with OV101

OV101 was generally safe and well tolerated in all Phase 2 and 3 studies that included more than 4300 subjects with insomnia (aged 18 to 64 years) who were administered doses up to 15 mg (20 mg in one early Phase 2 study). In adult subjects, the most common adverse events (AEs) that occurred more frequently in OV101-treated subjects than in subjects on placebo were dizziness, nausea, vomiting, somnolence, and headache. Most AEs were of mild to moderate intensity. Generally, tolerability was better in male subjects than in female subjects, most likely due to the lower body weight of females.

OV101 administration in the morning was safe at all doses (Study 99096). In healthy young men, doses up to 20 mg were well tolerated when given alone as single morning doses for 5 days. In young women, a 15 mg morning dose was not well tolerated or was tolerated with considerable discomfort from Day 2 onwards. An evening dose of 15 mg was well tolerated in young women and women above 55 years for 3 consecutive days. The AEs with the highest incidences in this study were dizziness, nausea, headache, and somnolence. The majority of AEs had a rapid onset (within 1 to 2 hours postdose) and resolved after the drug was discontinued.

Safety data from Study 11336 showed that 30 mg and 45 mg OV101 in women and 45 mg OV101 in men was not tolerated based on their history of hypnotic/sedative abuse or other drug abuse. This is contrary to previous experience with the same doses in healthy volunteers. These findings suggest that a history of hypnotic/sedative abuse or other drug abuse decreases the tolerability of supratherapeutic doses of gaboxadol. Adverse events that were associated with lack of tolerability included psychiatric events such as agitation, dissociation, hallucinations, disorientation, and anxiety.

Approximately 500 subjects were exposed to OV101 in clinical studies in non-insomnia-related development. The safety and tolerability profile of OV101 in the non-insomnia-related studies was similar to that in sleep disorder studies. In general, the AEs were dose related, with no AEs reported at the 5-mg dose and only mild AEs reported for the 10-mg dose of OV101.

Phase 2 and Phase 3 studies in adult subjects with primary insomnia demonstrated that OV101 is effective in restoring classical sleep parameters (sleep induction and sleep

Ovid Therapeutics Inc.

[figure not shown]
Protocol: OV101-17-001 Version 1.2

27 Mar 2019

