8.2.1.5 Sleep Diary

A paper sleep diary will be completed by each subject's LAR/caregiver, on behalf of the subject. Endpoints assessed by the sleep include how long it took the subject to fall asleep

(sleep onset latency [SOL]), the amount of time the subject was awake during the night (WASO), the total amount of sleep obtained (total sleep time [TST]), daytime sleepiness, defined as duration of napping in the daytime, and number of times subject woke up at night. The sleep diary will be completed each day during the 7 days immediately preceding each clinic visit after screening.

Sleep Parameters	Derivation
Sleep Onset Latency (SOL) in minutes	[First night: time to sleep – time subject went to bed) + (Second night: time to sleep – time subject went to bed) + (Third night: time to sleep – time subject went to bed) + (Fourth night: time to sleep – time subject went to bed) + (Fifth night: time to sleep – time subject went to bed) + (Sixth night: time to sleep – time subject went to bed) + (Seventh night: time to sleep – time subject went to bed)]/7 (or number of days with non-missing values) Note: For sleep time, consider the time closest on or after the time the subject went to bed on the same day
WASO (minutes)	Sum (time to sleep – time to wake from the previous log), considering all records between the time subject went to bed until subject woke up, then take the weekly average using the number of days with non-missing values.
TST (hours)	The weekly average, using the number of days with non-missing values, of total sleep time, converting the unit into hours.
Daytime Sleepiness (minutes)	The weekly average, using the number of days with non-missing values, of (time to sleep – time to wake), considering only records on the same day before subject went to bed
Number of times subject woke in the nights (counts)	The weekly average, using the number of days with non-missing values, of number of records from WASO considering all records between the time subject went to bed until subject woke up.

Weekly average of sleep parameters will be calculated with missing data excluded.

The baseline values of actigraphy parameters will be obtained from data collected within 7 days immediately preceding Day 1.

Change from baseline on the sleep parameters at Week 2, Week 6, and Week 12 will be analyzed as described in [Section 8.1](#).

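### Actigraphy WASO, awakenings and sleep onset latency are averaged per sleep interval while night sleep time is summed per day, so any split night, or any nap scored as sleep, would distort them

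*SAP*

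**What the plan says.** The derivation table in SAP 8.2.3.1 aggregates the same interval records in different ways.

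- Night total sleep time (TST): "Take Sum of sleep time (minutes) where interval type = 'sleep' within each day then the Mean of this sum". This is a per-day total, then an average over days.
- Day TST: "Take Sum of sleep time (minutes) where interval type = 'Active' within each day", again followed by an average.
- WASO: "Mean of WASO when interval type = sleep".
- Nocturnal awakenings: "Mean of # Wake bouts when interval type = sleep".
- SOL: "Mean of Onset Latency (minutes), duration from the beginning of the rest period to the start of sleep onset, reported when interval type = sleep".

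Sleep efficiency is also a plain mean over sleep-type records. No row gives a clock window, a rule for naps, or a rule for a night that holds more than one sleep interval. 'Day' is not defined for a night that crosses midnight, although the same section notes that the device stores data by clock time.

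The sleep diary (SAP 8.2.1.5) works differently. It describes WASO as "the amount of time the subject was awake during the night (WASO"), adds up wake time from going to bed to waking up, and only then takes the weekly average. It keeps naps apart as records before bedtime on the same day. SAP 8.2.3.1 says the actigraphy data will be compared with the diary data.

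**The concern.** WASO and awakenings are quantities per night. Averaging them over intervals gives a per-night value only when each night is exactly one interval. If a night is recorded as two intervals, the mean uses two partial values where it should use their sum, and the time awake between them belongs to neither. If a nap is scored as a sleep interval, it counts as night sleep, is missing from day sleep, and adds a short record to the averages for WASO, awakenings and SOL.

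The setting makes this worth closing. Protocol 1.2 cites sleep problems in 31% to 77% of individuals with FXS and more wake time after sleep onset in affected children. Daytime napping is a diary endpoint, and the device is worn day and night for 7 days (Protocol 6.3.3.1). The parameters go into the repeated-measures model of SAP 8.1, with pairwise regimen differences, to inform a future study. The comparison of the two sleep measures is also at risk, because WASO would have a different unit in each.

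**Working it through.** The documents give no worked actigraphy figure, so there is nothing to reproduce. The check applies the SAP 8.2.3.1 rules literally to one 7-day record.

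**From the documents:** 7 recorded days; TST summed per day and then averaged; WASO, awakenings and SOL averaged over all sleep-type records.

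**Assumed for illustration:** every night has 480 min (8 h) of sleep, WASO 60 min, 4 wake bouts and SOL 30 min. A nap scored as sleep lasts 60 min, with WASO 5 min, no wake bouts and SOL 10 min. Where a gap between two sleep intervals is counted, it is 60 min.

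**1. Split nights.** With k nights recorded as two intervals there are 7 + k records, and total within-interval WASO is still 7 × 60 = 420 min. The reported value is 420/(7 + k), that is, 60 × 7/(7 + k). Awakenings are 28/(7 + k). The within-night split does not matter: 30 + 30, 50 + 10 and 60 + 0 all average 30. A per-night WASO that counts the gap is (420 + 60k)/7.

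| Nights split (k) | WASO, SAP rule | Change from 60 | Awakenings, SAP rule | Per-night WASO with gap | SAP value as share |
|---|---|---|---|---|---|
| 0 | 60.0 | 0 | 4.0 | 60.0 | 100% |
| 1 | 52.5 | -12.5% | 3.5 | 68.6 | 77% |
| 3 | 42.0 | -30% | 2.8 | 85.7 | 49% |
| 7 | 30.0 | -50% | 2.0 | 120.0 | 25% |

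**2. Naps scored as sleep.** With m naps in the week and no split nights, night TST is (7 × 480 + 60m)/7 min, WASO is (420 + 5m)/(7 + m), awakenings are 28/(7 + m), and SOL is (210 + 10m)/(7 + m).

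| Naps (m) | Night TST (h) | WASO (min) | Awakenings | SOL (min) |
|---|---|---|---|---|
| 0 | 8.00 | 60.0 | 4.0 | 30.0 |
| 1 | 8.14 | 53.1 | 3.5 | 27.5 |
| 3 | 8.43 | 43.5 | 2.8 | 24.0 |
| 7 | 9.00 | 32.5 | 2.0 | 20.0 |

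The true night is the same in every row. None of the nap minutes reaches day TST, which reads only Active intervals.

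**3. Change from baseline.** If k is the same at baseline and at a later visit, both values carry the factor 7/(7 + k). No change appears where there is none, and a true change is shrunk by that factor (0.70 for k = 3). A spurious change needs k or m to move between visits. A spurious regimen difference needs them to move differently by regimen.

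**4. Summing per night first.** WASO stays at 60 min and awakenings at 4.0 for every k when there is no gap. With the gap counted, WASO takes the per-night values in the first table. Night TST stays at 8.00 h for every m.

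**The case against.** The strongest reply is that nothing in the documents shows naps scored as sleep or nights returned as several intervals. The table leans the other way. Day TST is read from Active intervals, so the authors seem to expect daytime sleep there. SOL and efficiency are tied to a rest period in bed. The sum-then-average wording for night TST also appears for Active-interval sleep and for activity counts, so it may be template text and not a sign that split nights were foreseen. The denominator of the WASO mean is not named. Upload is left to a study manual that is not among the documents. The endpoints are exploratory, SAP 11.1 treats all p-values as exploratory, and the diary already covers SOL, WASO, TST and awakenings per night.

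Most of this stands as a limit on frequency and importance. It does not supply the missing rule. A mean over sleep records is the literal reading, and the provider's convention invoked in the section is for missing data only.

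A reader might also infer that the error favours OV101, since the common adverse events in adults in Protocol 1.4 were "dizziness, nausea, vomiting, somnolence, and headache" and more napping would look like better nights. The documents do not support that. The same section reports no adverse events at the 5-mg dose in non-insomnia studies. Only the 15 mg/day regimen has an active afternoon capsule (Protocol Table 5-2), and there is no placebo group. An adverse event of somnolence does not show that naps increase or are scored as sleep. The split-night mechanism can run the other way: Protocol 1.4 reports better sleep maintenance in insomnia, and fewer split nights on treatment would raise reported WASO relative to baseline.

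**Conclusion.** The point holds as a conditional defect in the derivation rules. A split night enters the average at half its within-interval WASO and awakenings, and the wake time between its intervals disappears. A nap scored as sleep goes into night TST and dilutes the other three measures. The weekly effect on WASO is the factor 7/(7 + k) for equal nights split in two. The tempting summary that a split night halves WASO is right for that night only; the weekly figure halves only if all seven nights split. Nor does it follow that the subjects with the most broken nights show the best WASO, because waking inside a single sleep interval is still counted.

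How often either event occurs is not stated. The bias is zero with one sleep interval per night and no nap scored as sleep, and its direction is otherwise unknown. All minute values in the tables rest on the assumed night, nap and gap; the factor 7/(7 + k) needs only equal nights and two intervals per split night. The possible mismatch of units with the diary WASO comes from the same gap. This is a cheap improvement to exploratory endpoints. It does not touch the primary safety analysis.

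**What to change.** In SAP 8.2.3.1, derive every parameter per night first:

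- Define the night from the actigraphy record itself, as the main rest period within a noon-to-noon day. Do not anchor it to diary bed and wake times, so that the two sources stay independent for their comparison.
- Sum sleep time, WASO (including wake time between sleep intervals) and wake bouts within each night.
- Take SOL from the first sleep interval of the main rest period.
- Compute efficiency per night, as nightly sleep time over nightly rest time.
- Average each parameter over recorded nights.
- Assign sleep intervals outside the main rest period to TST during day.

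The cost is SAP wording and a small re-aggregation step on interval data already uploaded. The one new decision is how the main rest period is identified. That rule should also say when two rest periods in one night are joined, since otherwise the second part of a split night would be moved to day sleep. Where each night is one sleep interval and no nap is scored as sleep, WASO, awakenings, SOL and night TST are unchanged.

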6.1.2.1.2 Actigraph

Study staff will upload data from the subject's actigraph as described in the study manual and will review the quality of the data. If quality issues are detected, study staff will review proper use of the actigraph with the LAR/caregiver. Study staff will issue a fully charged, reset actigraph to the LAR/caregiver, including new hospital bands (if needed; Section 6.3.3), for use in the 7-day period preceding the Week 2 clinic visit. A calendar reminder will also be provided for the start of actigraph use.

Study staff will reset and recharge the actigraph received from the LAR/caregiver, and that reset and recharged actigraph will be issued for use by the next available subject and LAR/caregiver.

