6.3.3 Direct Subject Assessments

6.3.3.1 Actigraphy

Actigraphy is a noninvasive method of monitoring human rest/activity cycles. A small actigraph unit is worn to measure daytime and sleep activity. The actigraph unit stores motion data by clock time, and the data must be uploaded to an actigraphy database for analysis.

Each subject will be provided a wearable actigraph unit (Actiwatch; Philips Respironics Inc, Murrysville, PA), preferably to be worn on the nondominant wrist. If the subject is not able to tolerate the Actiwatch on his wrist, he may wear it on his ankle. The Actiwatch can be attached with a hospital band if that makes it more acceptable for the subject. Once a body location is selected for attachment of the Actiwatch, every effort should be made to keep the location the same throughout the study. Severe sensory sensitivities exist in the study population, and it is anticipated that some subjects will not be able to tolerate wearing the device. Therefore, if a subject is not able to tolerate the Actiwatch and/or comply with the Actiwatch guidelines, he may continue to participate in the study. The Actiwatch will be worn during the 7 days immediately preceding each clinic visit after screening. It should be

worn continuously throughout the day and night for 7 consecutive days. The actigraphy data (Section 7.3.3) will be compared to the sleep diary data.

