3.2.3.3 Direct Subject Assessment Endpoints

- Actigraphy parameters for sleep, including SOL, WASO, sleep fragmentation, number of nocturnal awakenings, TST, sleep efficiency, and daily activity level.
- Mean change from baseline in KiTAP subtest scores
- Mean change from baseline in RBANS subtest scores

3.2.3.4

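### Daily Activity Level is a raw daily sum of actigraphy counts with no allowance for time worn, so a change in wear reads as a change in activity

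*SAP*

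**What the plan says.** **Derivation.** The table in SAP 8.2.3.1 gives, for Daily Activity Level: "Take Sum of Total AC (counts) within each day then the Mean of this sum for an average score per day". The row names no interval type, no worn-time denominator, no minimum wear for a day to count and no minimum number of days. In the same table, sleep onset latency, WASO, nocturnal awakenings and sleep efficiency are means over sleep intervals. Night and day total sleep time (TST) are built like Daily Activity Level: a sum within each day, then a mean over days.

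**Analysis.** The section sends change from baseline at Weeks 2, 6 and 12 to the methods of SAP 8.1. It limits the baseline value to the 7 days before Day 1 but states no matching window for later visits. The schedule footnotes in both documents do ask for collection over the 7 days before each clinic visit.

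**Status.** SAP 3.2.3.3 lists the parameter among the exploratory endpoints: "Actigraphy parameters for sleep, including SOL, WASO, sleep fragmentation, number of nocturnal awakenings, TST, sleep efficiency, and daily activity level".

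**Wear.** Protocol 6.3.3.1 asks that the device be "worn continuously throughout the day and night for 7 consecutive days". It also says: "Severe sensory sensitivities exist in the study population, and it is anticipated that some subjects will not be able to tolerate wearing the device". It adds that "if a subject is not able to tolerate the Actiwatch and/or comply with the Actiwatch guidelines, he may continue to participate in the study".

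**Gaps in the data.** SAP 8.2.3.1 says: "Missing data convention from the provider will be used for missing assessments and scores"; otherwise data stay missing. The convention is not described. At site level, Protocol 6.1.2.1.2 says: "If quality issues are detected, study staff will review proper use of the actigraph with the LAR/caregiver". For the sleep diary, SAP 8.2.1.5 is explicit: "Weekly average of sleep parameters will be calculated with missing data excluded".

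**The concern.** A daily total depends on how long the device was recording as well as on how active the subject was. Hours off the device contribute nothing to the sum, yet the day still counts as one day in the mean. The rule that missing data stay missing does not reach this case, because a partly worn day produces a score.

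The study has no placebo group, so readers will look at change within each regimen and at the pairwise regimen differences that SAP 8.1 requests. If wear differs between baseline and follow-up, the change score contains that difference. If wear differs between regimens, so does the regimen contrast. A fall caused by less wear could be read as calmer behaviour or as sedation. A rise in wear could hide a true fall. SAP 8.1 says the modelling is meant to inform a future study, which is where a misread signal would do harm.

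**Working it through.** Neither document states an effect size, SD or wear rate for actigraphy, so there is no planned figure to reproduce. The check applies the SAP formula to a subject whose true activity does not change.

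**Inputs**
- Score = mean over days of the daily sum of counts (SAP 8.2.3.1).
- Intended wear: 24 hours a day for 7 days (Protocol 6.3.3.1).
- Assumed: full wear at baseline; *h* hours off the device per day at follow-up; counts spread evenly over *W* hours, with *W* = 24 or *W* = 16 (waking hours only).

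**Same loss every day.** Spurious change = (*W* − *h*)/*W* − 1 = −*h*/*W*.

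| Hours off per day | *W* = 24 | *W* = 16 |
|---|---|---|
| 2 | −2/24 = −8.3% | −2/16 = −12.5% |
| 4 | −4/24 = −16.7% | −4/16 = −25.0% |

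**Loss on some days only.** With *W* = 16 and 4 hours off on 2 of 7 days: (5×16 + 2×12)/7 = 14.86; 14.86/16 − 1 = −7.1%.

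**Whole days off.** If unworn days are scored zero, 1 day gives −1/7 = −14.3% and 2 days give −2/7 = −28.6%. If they are dropped as missing, the change is 0%. The SAP does not say which applies.

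**Opposite direction.** A true 10% fall with wear rising from 20 to 23 hours a day (*W* = 24): 0.90 × 23/20 − 1 = +3.5%. The fall appears as a rise.

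**After the change.** Counts per worn hour, taken over the hours in which counts occur, give (*W* − *h*)/(*W* − *h*) = 1, so 0% change in each partial-wear case. This needs non-wear to be unrelated to activity level. If counts occur only in 16 waking hours, all 4 lost hours are waking hours, and the denominator is all worn hours, the rate is (12/16)/(20/24) = 0.90. A 10% spurious fall remains, against 25% for the raw sum.

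**The case against.** The strongest reply is that the counts come from a provider's database, that the SAP puts the provider's convention ahead of leaving data missing, and that this convention or the study manual may deal with non-wear. This stands in part: what happens to unworn time is unstated, not known to be wrong. But marking off-device minutes as missing would not repair a sum, because the counts are still absent from it. Only a rule that drops or rescales incomplete days would, and none is given.

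The protocol also takes steps to protect wear: ankle placement, a hospital band, a consistent location, a check of the recording before randomization, and data review with re-instruction. These make large losses less likely. None of them adjusts a score.

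Several stronger readings are tempting and are not supported:

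- *That the whole population is expected to remove the device.* The protocol says some subjects. Those who never wear it have no data; the bias comes from partial wear.
- *That activity will appear to improve.* Nothing in the documents shows wear falling over time or differing by regimen, and the bias can run either way.
- *That motor hyperactivity is a named target of the drug in this trial, measured objectively only here.* The statement in Protocol 1.6 reports a knockout-mouse result. The trial measures hyperactivity through secondary scales (ABC-C, ADAMS, Conners 3), and Protocol Table 6-2 places actigraphy in the sleep domain.
- *That partial days when the device is put on or handed back lower the score by a set amount.* No start or stop hour is given, baseline is confined to the 7 days before Day 1, and a constant proportional loss would cancel in percent change. Only unequal handling between visits matters.

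Finally, a rate is not the same quantity as a daily total, and it is unbiased only under the condition shown above. That is a reason to keep the raw sum alongside it.

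**Conclusion.** The concern holds for an exploratory parameter. The stated rule gives too low a value for any partly worn day, the protocol foresees imperfect wear, and no described safeguard corrects it. Changes in wear between visits or regimens will therefore be confounded with changes in activity, with the direction unknown.

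Under the assumed 2 to 4 hours off per day the error is about 8% to 17% (counts over 24 hours) or 12.5% to 25% (counts in 16 waking hours). These sizes rest on assumed wear, full wear at baseline and constant true activity; the documents supply no wear data. The night and day TST sums share the weakness of having no valid-day rule. The primary safety objective and the secondary behaviour endpoints are not affected, and SAP 11.1 already treats all p-values as exploratory.

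**What to change.** Amend SAP 8.2.3.1 before database lock:

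1. State how non-wear is identified, including what the provider's convention does with unworn time.
2. Name the interval types summed for Daily Activity Level.
3. Use the same 7-day pre-visit window at baseline and Weeks 2, 6 and 12.
4. Set a minimum worn time for a valid day. Treat other days as missing, not as zero and not as full days. The documents offer no threshold, so the sponsor must choose and justify one.
5. Analyse counts per worn minute (or hour) on valid days. Keep the raw daily sum as a sensitivity result.
6. Apply the same valid-day rule to the night and day TST sums.
7. Report wear time by visit and regimen, so that readers can judge whether wear moved.

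The cost is SAP wording and programming, provided worn minutes can be recovered from the uploaded data, which neither document confirms. A few short-wear days or subjects will drop out of these exploratory parameters. The rate remains unbiased only if non-wear is unrelated to activity level, and the report should say so.
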